#### 6.5.2.5. Electrocardiograms

Electrocardiograms (12-lead) will be obtained at the time points described in the Schedule of Activities (Section 1.1). Electrocardiograms will be measured using standardized equipment provided by the central core laboratory with the patient in a semi-supine or supine position after 5 minutes of rest. The ECGs will be assessed by central review and a report provided to the site. The investigator or sub-investigator (or a qualified individual at the investigational site) will interpret the ECG report provided by the central reviewer using one of the following categories: normal or abnormal. The investigator or sub-investigator will judge if any of the findings are clinically significant.

#### 6.5.2.6. Bone Mineral Density

Bone mineral density is determined using DXA scanning and will be assessed at the lumbar spine (L1, L2, L3, and L4), total hip, and femoral neck (same leg within each patient) at the time points described in the Schedule of Activities (Section 1.1). The scans will be read by the central imaging laboratory in accordance with the imaging charter. Training, quality review, and readings will be done by a central radiology laboratory as described in the central radiology charter for bone mineral density.

Throughout the study, the same DXA apparatus will be used at each site and operated in the same scan mode for all scans for an individual patient and should be the same as used for the patient during the parent study (MVT-601-3101 and MVT-601-3102). The central core imaging laboratory will collect and evaluate all DXA scans for acceptability. Bone mineral density changes for individual patients will be monitored by the central imaging laboratory over the course of the study.

Determination of bone mineral density by DXA at the Early Termination visit or at the Week 104 visit and follow-up of findings will proceed according to the following rules:

#### Early Termination and 6-Month Post-Treatment DXA

- For patients who early terminate:
  - For Early Termination occurring **before Week 36**, DXA is not required at the Early Termination visit unless it will aid in the assessment of an adverse event or if the most recent DXA bone mineral density loss at lumbar spine (L1-L4) or total hip was > 2% relative to the parent study baseline. In this case, follow-up DXA is required at 6 months ( $\pm$  1 month).
  - For Early Termination occurring **at or after the Week 36 visit**, DXA is required at Early Termination unless a DXA result is available from within six weeks prior to Early Termination.

Most recent DXA was at the Week 24 visit: Follow-up DXA is required at 6 months ( $\pm 1$  month) if the most recent DXA scan was at Week 24 and bone mineral density loss at the lumbar spine (L1-L4) or total hip was  $> 2\%$ , relative to the parent study baseline;

Most recent DXA was after the Week 24 visit: Follow-up DXA is required at 6 months ( $\pm 1$  month) if, on the most recent DXA scan in the open-label extension study, bone mineral density loss at the lumbar spine (L1-L4) or total hip was  $> 3\%$ , relative to the parent study baseline.

### **Study Completion and 6-Month Post-Treatment DXA**

- For patients who complete the open-label extension study:

Follow-up DXA is required at 6 months ( $\pm 1$  month) if, at the Week 104 visit or on the most recent DXA scan, bone mineral density loss at the lumbar spine (L1-L4) or total hip was  $> 3\%$ , relative to the parent study baseline.

Note: Patients undergoing 6-month post-treatment follow-up should also have the following clinical laboratory evaluations: vitamin D, thyroid-stimulating hormone, parathyroid hormone, creatinine, calcium, and phosphorous.

### **Patients Who Have Previously Completed or Early Terminated from the Study**

Patients who have previously completed or early terminated from the study prior to Protocol Amendment 3.1 may not have undergone post-treatment DXA according to the current protocol requirements. To allow for further follow-up of these patients, it is strongly recommend that attempts be made to contact the patients who met the protocol specified threshold of  $> 3\%$  bone loss at or after the Week 36 DXA scan to obtain a post-study follow-up DXA scan at 6 months ( $\pm 1$  month) from last dose of study drug, if such a scan has not been scheduled or performed. For patients who are already out of this 6-month window, an unscheduled post-treatment follow-up DXA scan is recommended.

### **12-Month Post-Treatment DXA**

- If patients have 6-month post-treatment follow-up scans that show bone loss of  $> 1.5\%$  at the lumbar spine and/or  $> 2.5\%$  at total hip compared with the parent study baseline, patients are strongly encouraged to come back to the clinic for an additional post-treatment follow-up scan 12 months from the date of the last dose of the study drug. Patients undergoing 12-month post-treatment follow-up should also have the following clinical laboratory evaluations: vitamin D, thyroid-stimulating hormone, parathyroid hormone, creatinine, calcium, and phosphorous.
- If patients have 12-month post-treatment follow-up scans that show bone loss of  $\geq 3\%$  at the lumbar spine and/or total hip compared with the parent study baseline, patients are recommended to be referred to and strongly encouraged to see a bone specialist for further evaluation or the bone loss.

Note 1: Patients undergoing 6-month post-treatment follow-up should also have the following clinical laboratory evaluations: vitamin D, thyroid-stimulating hormone, parathyroid hormone, creatinine, calcium, and phosphorous.

Note 2: When a patient is referred to a bone specialist for evaluation and management, Myovant will provide a Bone Consultation Letter to the investigator for this additional bone consult and will request the site to provide a summary of the evaluation and management plan once the consultation is complete.

#### **6.5.2.7. Endometrial Biopsy**

For patients in parent study MVT-601-3101, an endometrial biopsy is performed at the Week 24 visit. If the required Week 24 biopsy is inadequate for diagnosis, it should be repeated, and a sample submitted to the central laboratory. If the second sample is inadequate, ensure an endometrial thickness has been reported from the Week 24 transvaginal ultrasound and contact the medical monitor to review the findings.

Patients who have endometrial hyperplasia or endometrial carcinoma will be withdrawn from study drug treatment and followed per instructions in the parent and/or extension study protocol.

Additional assessment of the effects of relugolix co-administered with low-dose estradiol and norethindrone acetate on the endometrium will be performed at the Week 52 and Early Termination visit for all patients. An endometrial biopsy is required for all patients at the Early Termination visit except for patients whose last dose of study drug was taken during Week 32 or earlier or within four weeks after completion of the Week 52 endometrial biopsy. However, the endometrial biopsy may be obtained if it will aid in the evaluation of an ongoing adverse event. An endometrial biopsy at Week 104 is recommended for all patients who complete the open-label extension; however, patients will have the option to opt out. Patient participation in the Week 104 endometrial biopsy is voluntary and refusal to participate will not indicate withdrawal from the study.

The Week 52, Week 104, and Early Termination endometrial biopsy samples will be submitted to the central laboratory. If the Week 52, Week 104, or Early Termination biopsy specimen is inadequate, a transvaginal ultrasound for endometrial thickness should be obtained and read locally. The transvaginal ultrasound findings will be used to determine if further action is required:

- Endometrial thickness  $\leq 5$  mm: no further action required;
- Endometrial thickness  $> 5$  mm at any location or any other endometrial abnormality: repeat endometrial sampling. Contact medical monitor if second specimen is inadequate for diagnosis.

Investigators should contact the medical monitor if a patient refuses to have an endometrial biopsy at Week 52 or the Early Termination visit. Unscheduled endometrial biopsies may also be performed when medically indicated and as deemed necessary by the investigator. The investigator should obtain approval from the sponsor to perform an unscheduled endometrial biopsy, unless urgently indicated. Additional consent is not required in this circumstance.

#### **6.5.2.8. Status of Menstruation Recovery**

If the first menstruation after the end of study treatment administration is observed before the Follow-Up visit, the date of onset of the first menstruation is recorded in the eCRF. Patients whose menses has not resumed as of the Follow-Up visit for whom there is no explanation for the lack of resumption (eg, medical procedure or medications) will be contacted by telephone

3 months (+ 0.5 months) after the Follow-Up visit to determine if menses has resumed and will be asked about factors that may affect resumption of menses. If a patient is lost to follow-up, three documented attempts should be made to contact the patient by telephone. If unable to contact the patient by telephone, a certified letter must be sent to the patient.

If the patient enrolls directly into another relugolix clinical study upon completion of the Week 104 visit, follow-up under this protocol to determine the status of menstruation recovery may not be required.

#### **6.5.2.9. Mammogram**

A mammogram will be performed at the Week 52 or Week 104/Early Termination visit (see the Schedule of Activities in Section 1.1) for patients  $\geq 40$  years of age at the time of the visit. If a patient had a recent mammogram per standard of care within the 6 months before Week 52 that was Breast Imaging Reporting and Data System category 1 or 2 or equivalent or had benign findings, as determined by the investigator or medical monitor, a mammogram is not required at Week 52 but should be completed by Week 104/Early Termination. If a patient turns 40 years old after the Week 52 visit has occurred, a mammogram should be performed no later than the Week 104/Early Termination visit.

All mammogram results will be read locally using Breast Imaging Reporting and Data System categories or equivalent (see [Appendix 8](#)) and recorded in the eCRF. The following actions will be taken depending on the reading:

- Category 1 or 2 or equivalent: normal mammogram; no further action is required unless determined by the investigator or medical monitor;
- Category 0 or 3 or equivalent: adjunctive breast imaging or follow-up mammogram will be required, and the investigator should contact the medical monitor for approval of additional breast imaging;
- Category 4 to 6 or equivalent: the investigator should contact the medical monitor within 24 hours.
- Patients who have malignant breast lesion(s) or breast carcinoma will be withdrawn from study drug treatment (see Section 4.5).

---

## 7. SAFETY CONSIDERATIONS

Study assessments of safety include adverse events, vital signs and weight, physical examinations, clinical laboratory tests, ECGs, and bone mineral density assessments.

### 7.1. Adverse Event Definitions

#### 7.1.1. Adverse Event

Adverse event: An adverse event is any unfavorable and unintended sign (including an abnormal laboratory finding), symptom, or disease (new or exacerbated) temporally associated with the use of a medicinal product, whether or not related to the medicinal product.

Events meeting the definition of an adverse event **include**:

- A worsening, excluding minor fluctuations, in the nature, severity, frequency, or duration of a pre-existing condition;
- Development of an intercurrent illness during the study;
- Development of symptoms that may or may not be related to the use of a concomitant medication or investigational product;
- Injury or accidents: If a medical condition is known to have caused the injury or accident, the medical condition and the accident should be reported as 2 separate medical events (eg, for a fall secondary to dizziness, both “dizziness” and “fall” should be recorded separately); and
- An investigational abnormality (eg, laboratory parameter, vital sign, ECG) only if the abnormality is considered clinically significant by the investigator based on at least one of the following criteria:
  - Induces clinical signs or symptoms;
  - Requires active intervention;
  - Requires interruption or discontinuation of study drug.

Events that **do not** meet the definition of an adverse event include:

- Medical or surgical procedures (eg, surgery, endoscopy, tooth extraction, transfusion); the condition that leads to the procedure is an adverse event;
- Pre-existing diseases or conditions present or detected before the start of study drug administration that do not worsen;
- Situations where an untoward medical event has not occurred (eg, planned hospitalization for an elective procedure, with elective defined as known or planned at the time of signing of the informed consent);
- Endometriosis-associated pain is not considered an adverse event in this study because it is being quantitatively measured as the primary efficacy endpoint.

Adverse events that occur during the study should be evaluated by the investigator and graded according to the National Cancer Institute Common Terminology Criteria for Adverse Events

(CTCAE). Episodic adverse events, such as vomiting, or those that occur repeatedly over a period of consecutive days are “intermittent”. All other events are “continuous”. Additional information on detecting, documenting, and reporting adverse events and serious adverse events are provided below.

### 7.1.2. Serious Adverse Event

A serious adverse event is any untoward medical occurrence that, at any dose:

- a. Results in death;
- b. Is life-threatening;  
NOTE: The term “life-threatening” in the definition of “serious” refers to an event in which the study participant was at risk of death at the time of the event. It does not refer to an event, which hypothetically might have caused death, if it were more severe. For example, drug-induced hepatitis that resolved without evidence of hepatic failure would not be considered life-threatening even though drug-induced hepatitis can be fatal.
- c. Requires hospitalization or prolongation of existing hospitalization;  
NOTE: In general, hospitalization signifies that the patient has been admitted to a hospital, independent of the duration of that hospitalization. Complications that occur during hospitalization are adverse events. If a complication prolongs hospitalization or fulfills any other serious criteria, the event is serious. When in doubt as to whether “hospitalization” occurred or was necessary, the adverse event should be considered serious. Hospitalization for elective treatment of a pre-existing condition that did not worsen from baseline is not considered an adverse event.
- d. Results in persistent or significant disability/incapacity;  
NOTE: The term disability means a substantial disruption of a person’s ability to conduct normal life functions. This definition is not intended to include experiences of relatively minor medical significance such as uncomplicated headache, nausea, vomiting, diarrhea, influenza, and accidental trauma (eg, sprained ankle) which may interfere or prevent everyday life functions but do not constitute a substantial disruption.
- e. Is a congenital anomaly/birth defect;
- f. Important medical events which jeopardize the patient and may require medical or surgical intervention to prevent one of the outcomes listed above. Examples of such events are invasive or malignant cancers, intensive treatment in an emergency room or at home for allergic bronchospasm, blood dyscrasias or convulsions that do not result in hospitalization, or development of drug dependency or drug abuse.

## 7.2. Adverse Event Reporting

The reporting of serious adverse events by the sponsor (Myovant Sciences GmbH) to regulatory authorities is a requirement and each authority has a timetable for reporting these events based upon established criteria. Likewise, it is the responsibility of the investigator to report serious adverse events to their local Institutional Review Board (IRB) or Independent Ethics Committee (IEC).

Care will be taken not to introduce bias when detecting adverse events and/or serious adverse events. Open-ended and non-leading verbal questioning of the patient is the preferred method to inquire about adverse event occurrence. Appropriate questions include:

- “How are you feeling?”
- “Have you had any (other) medical problems since your last visit/contact?”
- “Have you taken any new medicines, other than those provided in this study, since your last visit/contact?”

The patient’s eDiary entries, including bleeding and answers to the other patient-reported outcome measures, will not be used as a primary means to collect adverse events, however they should be reviewed by the study site personnel and the study monitors. Should the investigator or site staff become aware of a potential adverse event through the information collected with these instruments, proper follow-up with the patient for medical evaluation should be undertaken. Through this follow-up, if it is determined that an adverse event not previously reported has been identified, normal reporting requirements should be applied.

All patients who experience an adverse event will be evaluated at appropriate time intervals until the event resolves or has stabilized or become chronic. At the conclusion of the study, the investigator and medical monitor will assess unresolved adverse events and determine if additional follow-up is warranted.

All adverse events, whether or not related to the study drug treatment, must be fully and completely documented on the adverse event case report form and in the patient’s source documents. In addition, any adverse event resulting in permanent treatment discontinuation must be recorded on the appropriate case report form as well as documented in the patient’s source documents. Adverse event terms should include a diagnosis, as available, in preference to listing the individual signs and symptoms. If the diagnosis is not known, the investigator should record each sign and symptom as an individual adverse event.

Overdose and pregnancy in the patient will be reported as described in Section 7.7 and Section 7.8, respectively.

### **7.2.1. Adverse Event Reporting Period**

Adverse events and serious adverse events will be collected under this extension study protocol from the administration of the first dose of extension study drug until the Follow-up visit approximately 30 days after the last dose of study drug or the date of initiation of another investigational agent or hormonal therapy affecting the hypothalamic-pituitary-gonadal axis or surgical intervention for endometriosis, whichever occurs first, as also specified in the study Schedule of Activities (Section 1.1). Serious adverse events reported to the investigator after the safety reporting period should be reported to the sponsor regardless of causal relationship to study drug treatment.

Reporting instructions for serious adverse events are provided in Section 7.6.

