#### **4.5. Removal of Patients from Therapy**

Completion of the Week 104 visit defines completion of the study. Patients may withdraw consent to participate in the study and discontinue treatment at any time for any reason. Investigators or the medical monitor may remove patients from therapy under this protocol for reasons of safety and/or lack of compliance as discussed below. Patients removed from therapy for any reason will undergo the assessments for the Early Termination visit (see the Week 104 visit on the Schedule of Activities, Section 1.1) and will have a Follow-up visit to assess safety approximately 30 days after the end of study drug treatment (ie, after the patient's last dose of study medication). When patients complete the study or early terminate from the study, they must be deactivated from the study in the interactive voice response system/interactive web response system (IVRS/IWRS), eDiary, and tablet device.

The following safety and/or compliance events will result in the removal of patients from therapy either permanently or until the etiology of the problem has been identified and resolved:

- Any adverse event that is intolerable to the patient and that cannot be ameliorated by the use of adequate medical intervention, or that in the opinion of the investigator or medical monitor would lead to undue risk to the patient if dosing continued;
- If it is discovered after enrollment that a patient failed to meet protocol entry criteria and continued participation poses an unacceptable risk to the patient's health;
- If the following liver test abnormalities develop, study drug should be discontinued immediately with appropriate clinical follow-up (including repeat laboratory tests, until a patient's laboratory profile has returned to normal/baseline status):
  - ALT or AST > 8 x ULN; or
  - ALT or AST > 5 x ULN and persists for more than 2 weeks; or
  - ALT or AST > 3 x ULN in conjunction with elevated total bilirubin > 2 x ULN or international normalized ratio (INR) > 1.5; or
  - ALT or AST > 3 x ULN with appearance of fatigue, nausea, vomiting, right upper quadrant pain or tenderness, fever, rash and/or eosinophilia (> 5%);

- 
- QT interval by the Fridericia correction (QTcF) prolongation of more than 500 msec read by a cardiologist;
  - Evidence of endometrial hyperplasia or endometrial carcinoma on endometrial biopsy;

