## 5.10. Prior and Concomitant Medications and Non-Drug Therapies

### 5.10.1. Prohibited Medications

Table 5-2 provides examples of prohibited drug categories; however, it is not a comprehensive list of all restricted medications. Drugs and drug classes in Table 5-2 are prohibited at any time during the study through the Follow-Up visit, except as noted in the table. Consult the medical monitor if there is any uncertainty regarding patient use of a particular drug or drug class.

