### 5.10.3. Prohibited Non-Drug Therapies

Surgical treatment of endometriosis is prohibited from the Week 24/Baseline visit until the patient's final study visit unless urgently needed for patient safety.

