An endometrial biopsy will have been performed at the parent study Week 24 visit for all patients who participated in MVT-601-3101 (see MVT-601-3101 protocol for details). An endometrial biopsy is required at Week 52 and the Early Termination visit for all patients. This procedure is not required at the Early Termination visit in patients whose last dose of study drug was taken during Week 32 or earlier or within four weeks after completion of the Week 52 endometrial biopsy. However, the procedure may be done if it will aid in the evaluation of an ongoing adverse event. An endometrial biopsy at Week 104 is recommended for all patients who complete the open-label extension; however, patients will have the option to opt out. Safety monitoring for this study includes physical examination, clinical laboratory tests, pregnancy tests, and adverse event collection at each visit. Clinical chemistries will be collected at each visit. A complete blood count will be collected at Week 24/Baseline, Week 28, Week 36, Week 52, Week 65, Week 78, Week 91, and Week 104/Early Termination. At the Week 24/Baseline

visit, Week 52 visit, and Week 104/Early Termination visit, additional tests include fasting (at least 8 hours, other than water) glucose, lipid profile, and hemoglobin A1c.

Electrocardiograms will be performed at the Week 24/Baseline, Week 52, and Week 104/Early Termination visits.

A mammogram will be performed at Week 52 or at Week 104/Early Termination for women who are or become  $\geq 40$  years old during the study (see Section 6.5.2.9).

Bone densitometry will occur at the Week 24/Baseline, Week 36, Week 52, and Week 104/Early Termination visits. Follow-up of bone densitometry findings will proceed according to the rules described in Section 6.5.2.6.

Bone densitometry and ECGs will be submitted for central reading.

Study drug compliance will be reviewed at each visit. Fasting (other than water) for at least 8 hours is required prior to blood sampling on Week 24/Baseline and Week 52/Early Termination visits and for 1 hour after administration of the study drug in the clinic. Laboratory requisitions must indicate whether or not the patient was not fasted for their chemistry and lipid testing.

Refer to the Schedule of Activities (see Section 1.1) for information about study procedures during the Open-Label Treatment Period.

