## 9.5. Safety Analyses

Safety assessments will include treatment-emergent adverse events, vital signs and weight, physical examinations, clinical laboratory tests, 12-lead ECG, bone mineral density with DXA, mammograms (for patients required to have this procedure, see Section 6.5.2.9), and endometrial biopsy. Safety summaries by treatment group will be performed using treatment groups defined based on the actual randomized treatment received in the parent study.

The treatment-emergent period will be defined as the period of time from the first dose date and time of randomized study drug in the parent study through 30 days after the last dose of study drug, or the date of initiation of another investigational agent or hormonal therapy affecting the hypothalamic-pituitary-gonadal axis or surgical intervention for endometriosis, whichever occurs first. Safety will be assessed through summaries of adverse events, the frequency of treatment discontinuations due to adverse events, laboratory evaluations, and bone densitometry results.

The severity of all adverse events is to be evaluated by the investigator based on the National Cancer Institute CTCAE. All adverse events will be coded to preferred term, high level term, and system organ class using MedDRA 20.0 or higher. The incidence of adverse events will be presented by MedDRA system organ class and preferred term, relationship to study drug treatment, and severity. A patient reporting the same adverse event more than once is counted

once, and at the maximum severity or strongest relationship to study drug treatment when calculating incidence.

Laboratory data consist of chemistry, hematology, and hormonal tests. Only data collected by the central laboratory will be used to do the analyses. The National Cancer Institute CTCAE will be used to categorize toxicity grade for the laboratory parameters. Shift tables will be provided for each gradable parameter to summarize baseline toxicity grade versus post-baseline toxicity grade. For laboratory parameters that are not gradable by the CTCAE, a shift table based upon the normal range (low, normal, and high) will be provided for each parameter to summarize the parent study Baseline versus post-baseline results. All data will be listed and summarized by visit. The change from parent study Baseline to each post-baseline study visit will be presented by parent study treatment group for each laboratory test.

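### Adverse event collection and the treatment-emergent period can close at endometriosis surgery or hormonal therapy while study drug continues, and the protocol's collection instructions then conflict

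*Protocol*

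**What the plan says.** **Collection window (Section 7.2.1).** Collection starts at the first extension dose. It ends at the Follow-up visit about 30 days after the last dose, or on the start date of another investigational agent "or hormonal therapy affecting the hypothalamic-pituitary-gonadal axis or surgical intervention for endometriosis, whichever occurs first". The section says the Schedule of Activities specifies the same period. It then adds: "Serious adverse events reported to the investigator after the safety reporting period should be reported to the sponsor regardless of causal relationship".

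**Treatment-emergent window (Section 9.5).** This opens with the parent study's first randomized dose and extends "through 30 days after the last dose of study drug, or the date of initiation of another investigational agent or hormonal therapy", with endometriosis surgery as a further trigger and the earliest date governing.

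**The triggers during treatment.** Section 5.10.3 prohibits surgical treatment of endometriosis until the "final study visit unless urgently needed for patient safety". On hormonal products, Section 5.10.1 states: "Drugs and drug classes in Table 5-2 are prohibited at any time during the study through the Follow-Up visit".

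**Removal from therapy (Section 4.5).** The list opens with "The following safety and/or compliance events will result in the removal of patients from therapy either permanently or until the etiology". It names neither endometriosis surgery nor use of a prohibited hormonal product.

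**Collection by visit.** Section 6.2 says: "Safety monitoring for this study includes physical examination, clinical laboratory tests, pregnancy tests, and adverse event collection at each visit". The Schedule of Activities marks adverse event collection at every visit. Its footnote aa gives a start of collection and no stop at surgery or hormonal therapy.

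**The concern.** A safety window normally covers all time on drug plus a short tail, and a confounding therapy or operation may shorten the tail. Here the condition that dosing has ended is missing from both definitions, so a trigger during treatment closes both windows at once. Two things follow:

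- **Analysis.** An event with onset on study drug after that date is not treatment-emergent under Section 9.5, however serious it is. Surgery or added hormones may reflect poor pain control or a complication, so time dropped this way is plausibly not a random sample of exposure.
- **Conduct.** A site following Section 7.2.1 would stop recording non-serious events; a site following Section 6.2 and the Schedule would carry on. Incidence of adverse events is a named safety endpoint, so what is recorded should not depend on which section a site reads.

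**Working it through.** The plan states no figure to reproduce. The check is a comparison of the passages, followed by an illustration for a single patient.

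**1. Is the cut-off limited to the time after the last dose?** No. In Sections 7.2.1 and 9.5 the post-dose limit and the three triggers are alternatives, and the earliest governs. A trigger during dosing always precedes 30 days after the last dose, so it governs whenever it occurs on treatment.

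**2. Can a trigger occur on treatment?** Surgery can, under the urgent exception in Section 5.10.3. Hormonal therapy is prohibited, but a breach is possible.

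**3. Does a trigger end dosing?** Not by any listed rule. Section 4.5 names neither trigger, and its examples of gross noncompliance concern study drug, visits and the eDiary. The investigator or medical monitor keeps discretion to remove a patient, so continued dosing is possible but not prescribed.

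**4. Do the other sections repeat the cut-off?** Section 7.2.1 says the Schedule does. The Schedule and footnote aa do not, and neither does Section 6.2.

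**5. What happens to an on-drug event after the trigger?**

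| Type of event | Section 7.2.1 | Section 6.2 and Schedule | Section 9.5 |
|---|---|---|---|
| Non-serious | Outside the collection period | Collected at every visit | Not treatment-emergent |
| Serious | Outside the period, but still sent to the sponsor if reported to the investigator | Collected at every visit | Not treatment-emergent |

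**6. Size for one patient.** Assume a trigger at Week w and dosing to Week 104. The open-label period is 80 weeks, or 80 × 7 = 560 days.

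- On-drug days outside the window = (104 − w) × 7.
- With the 30-day tail = (104 − w) × 7 + 30, out of 560 + 30 = 590 days.

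| Trigger | On-drug days outside | Share of 560 | With tail | Share of 590 |
|---|---|---|---|---|
| Week 36 | 68 × 7 = 476 | 85% | 506 | 86% |
| Week 52 | 52 × 7 = 364 | 65% | 394 | 67% |
| Week 78 | 26 × 7 = 182 | 33% | 212 | 36% |

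The Section 9.5 window starts in the parent study, so its full length is 104 × 7 + 30 = 758 days. Against that, the shares with the tail are 506/758 = 67%, 394/758 = 52% and 212/758 = 28%.

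If the cut-off applied only after the last dose, a full-course patient would keep all 590 extension days whenever an on-treatment trigger occurred, provided there was no further trigger in the 30-day tail.

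**The case against.** The strongest reply is that the clause was only meant to trim the post-treatment tail. Section 6.3 uses the same kinds of event to bring the Follow-Up visit forward, and Section 4.6 discusses hormonal contraception from 4 weeks after the last dose. During treatment both triggers are prohibited or exceptional, and women who expect or want surgery are not eligible. This stands as evidence of intent. It does not supply the missing condition, and it supports writing that condition in.

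Ending a treatment-emergent window at a confounding therapy is also a defensible convention. That holds for the tail. It is harder to defend for time on study drug, where a flag deals with the confounding and keeps the event.

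A reader might go further and infer either of two things that the protocol does not support:

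- **That later on-treatment events are lost.** Serious events reported after the period still go to the sponsor. Section 7.2 requires all adverse events to be fully documented, and Section 6.2 and the Schedule continue collection. What is shown is a contradiction, with possible non-collection of non-serious events.
- **That discontinuations due to adverse events are understated.** Section 7.2 requires any event that leads to permanent discontinuation to be recorded on a case report form. Section 9.5 does not restrict the discontinuation count to treatment-emergent events.

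It is also open to interpretation whether one short hormonal exposure, such as emergency contraception, counts as starting hormonal therapy. The surgery case is firmer.

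Finally, the statistical analysis plan, which was not available here, could define treatment-emergent differently. It could not recover events that sites stopped recording because of Section 7.2.1.

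**Conclusion.** The point holds as a drafting gap with real but limited consequences. Read literally, Sections 7.2.1 and 9.5 let both windows close while dosing continues. On-drug events after that date, serious ones included, then fall outside the treatment-emergent period, and sites receive contradictory instructions on non-serious events.

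For an affected woman the excluded share is large: 65% of open-label days for a trigger at Week 52, if she stays on drug to Week 104. Continued dosing is an assumption that rests on the absence of a removal rule; the protocol does not prescribe it. No frequency is given, and because the triggers are prohibited or exceptional the number of women is probably small. No effect on overall incidence can be quantified. The correction is worth making because it is cheap and matches the apparent intent.

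**What to change.** - **Sections 7.2.1 and 9.5.** State that a new investigational agent, hormonal therapy or endometriosis surgery ends the window only if it occurs after the last dose of study drug. State also that every event with onset while the patient is taking study drug is collected and is treatment-emergent.
- **Flag.** Mark events that follow on-treatment surgery or hormonal use, so that they can be examined separately.
- **Alignment.** Give Section 6.2 and footnote aa of the Schedule the same end of collection, so that the cross-reference in Section 7.2.1 becomes true.

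This takes a sentence in each of the two sections, a footnote edit and a programming rule. Collection is already scheduled at every visit, so no new procedure is needed. The small downside is that some confounded events enter the tables, identified by the flag. Nothing here takes a position on whether study drug should continue after surgery or hormonal use.
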